10.3. Eastern Cooperative Oncology Group Performance Status

Shift tables from baseline to best post baseline in ECOG performance score will be displayed by disease cohort and treatment arm for the ITT Population.

CCI [REDACTED]

[REDACTED]

[REDACTED]

CELGENE PROPRIETARY INFORMATION

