### Overview of Key Safety Assessments

- Adverse Events(AEs) including adverse events of special interest (AESIs)
- Physical examination
- Vital signs, and body weight measurement
- Eastern Cooperative Oncology Group (ECOG) performance status
- Hematology (CBC with differential and platelets)
- Coagulation parameters
- Serum chemistry (includes amylase and lipase)
- Thyroid function tests
- Concomitant medications, therapies, and procedures
- Pregnancy testing (for females of childbearing potential [FCBP] only)
- Electrocardiogram (ECG)
- Urinalysis

Azacitidine and durvalumab are generally well tolerated without anticipated overlapping toxicities. Azacitidine causes well described gastrointestinal and hematologic AEs in the form of cytopenias and durvalumab has a low frequency of immune-mediated adverse events similar to other immune checkpoint agents (See section 1.4).

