### 3.2.2.1. Scheduled Assessments

All screening/baseline assessments and procedures must be performed prior to randomization.

Safety assessments will include: physical examination with vital signs including body weight, ECOG performance status, and evaluation for AEs, laboratory evaluations, blood chemistries including lipase/amylase and thyroid function, complete blood cell count (CBC), pregnancy testing, coagulation tests, electrocardiogram (ECG), [REDACTED] pharmacokinetics and urinalysis.

Efficacy assessments will include bone marrow aspiration and biopsy, CBC with differential, cytogenetics, and transfusion records.

For more details on the evaluations and schedule, refer to the Table of events (Section 5).

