## **9.7. Safety Analysis**

All subjects in the safety population who receive at least one dose of any assigned IP, will be included in the safety analyses. Adverse events, vital sign measurements, physical exam findings, clinical laboratory data, ECG interpretations, pregnancy tests for FCBP, concomitant

medications and procedures will be tabulated and summarized by treatment arm, and cohort, as appropriate.

Adverse events will be coded using Medical Dictionary for Regulatory Activities (MedDRA). Adverse event listings will include the verbatim term and the MedDRA preferred term. Adverse events will be graded according to CTCAE Version 4.03 criteria ([Appendix G](#)).

The frequency of AEs will be tabulated by MedDRA SOC and PT. In the by-subject analysis, a subject having the same event more than once will be counted only once. Adverse events leading to discontinuation from treatment, events leading to dose reduction/interruption/delay, events classified as CTCAE Version 4.03 Grade 3 or higher, IP-related events, AESI, imAEs and serious AEs will be tabulated and listed separately. By-subject listings of all AEs, and AESIs, serious AEs, and their attributes will be provided.

Clinical laboratory results will be summarized descriptively and will include a display of change from baseline. Laboratory values outside of the normal ranges will be identified. Laboratory data will be graded according to CTCAE Version 4.03 criteria for select analytes unless otherwise specified. The frequencies of the worst severity grade observed during treatment will be displayed in cross-tabulations by screening status. Clinically significant hematologic and nonhematologic laboratory abnormalities that meet Grade 3 or Grade 4 criteria according to CTCAE Version 4.03 will be listed and summarized.

Vital signs and ECG data will be summarized by cross-tabulations presenting normal and abnormal values by number of subjects at pre-and post-IP initiation.

Graphical displays will be provided where useful in the interpretation of results.

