7.2. Baseline Characteristics

Baseline clinical characteristics include temperature (°C), systolic blood pressure (SBP, mmHg), diastolic blood pressure (DBP, mmHg), pulse (bpm), respiratory rate, Eastern Cooperative Oncology Group (ECOG) performance status (PS) and baseline electrocardiograms (ECGs) will be summarized.

Coagulation test performed at screening will be summarized. Overall interpretation from coagulation test will be summarized along with prothrombin time/international normalized ratio, activated partial thromboplastin time, and thrombin time.

Baseline laboratory assessments from central laboratory will be summarized for Hgb, platelet count, absolute neutrophil count (ANC), white blood cell (WBC) count, creatinine, aspartate aminotransferase (AST/SGOT), alanine aminotransferase (ALT/SGPT) and total bilirubin.

Creatinine clearance (CrCl) will be assessed at screening by the central laboratory. Creatinine clearance is estimated using the Cockcroft-Gault formula where $CrCl(mL/min) = (140 - \text{age}) (\text{weight [kg]}) / 72 (\text{serum creatinine [mg/dL]})$; for females, the formula is multiplied by 0.85 (Cockcroft, 1976). The CrCl will be summarized as continuous variable. The creatinine clearance will be normalized to an average surface area (size) of 1.73m². The corrected CrCl will be summarized as continuous variable and category variable defined as chronic kidney disease (CKD) stages (Stage 1, 90+; Stage 2, 60-89; Stage 3, 30-59; Stage 4, 15-29; Stage 5, <15).

Cytogenetic risk classifications ([Appendix 17.4](#) and [17.5](#)) will be summarized with frequency counts and percentages. For MDS cohort, IPSS-R will be summarized along with hemoglobin, platelet and absolute neutrophil count used in the derivation. Bone marrow blast will be summarized as continuous variable and category variable as defined in IPSS-R ($\leq 2\%$; $> 2\% - < 5\%$; $\geq 5\% - \leq 10\%$; $>10\%$).

Baseline RBC transfusion burden and platelet transfusion burden will be summarized. The baseline transfusion burden is defined the total number of units of transfusion received before or on the first dose date. Only RBC transfusions given for hemoglobin of ≤ 9.0 g/dL before or on the first dose date will count in the baseline RBC transfusion burden.

The time from initial diagnosis to randomization will also be summarized.

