12. SAFETY ANALYSIS

This section defines the safety parameters for the study. All summaries of safety data will be conducted using the Safety Population. Descriptive statistics will be provided by disease cohort and treatment arm.

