12.2. Clinical Laboratory Evaluations

Descriptive statistics of observed and change from baseline values will be presented.

Clinical laboratory values will be graded according to CTCAE Version 4.03 or higher for applicable tests. Baseline grade and worst grade during treatment for selected laboratory results will be summarized. Shifts from baseline to the worst grade observed during the treatment for selected laboratory results will also be provided.

Clinically significant hematologic and nonhematologic laboratory abnormalities that meet Grade 3 or Grade 4 criteria according to CTCAE Version 4.03 will be listed and summarized. Listings of clinical laboratory data from central laboratory with abnormal flags will be provided by subjects and tests.

Listings of clinical laboratory data from central laboratory with abnormal flags will be provided by subjects and tests. Listings will also be provided for the local laboratory data.

CCI

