12.4. Vital Sign Measurements

For vital signs with shifts from baseline to worst during treatment (below, within, and above the normal ranges) will be displayed in cross-tabulations. Summary statistics (N, Mean, STD, median, Q1, Q3 Min, and Max) of observed and change from baseline values will be presented.

Normal ranges are defined as follows:

- Systolic blood pressure (SBP) → Normal (100 – 140 mm Hg, inclusive)
- Diastolic blood pressure (DBP) → Normal (60 – 90 mm Hg, inclusive)
- Body temperature → Normal (35 – 38°C, inclusive)
- Pulse → Normal (60 – 100 bpm, inclusive)
- Respiration → Normal (12 – 20 BPM, inclusive).

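### The only visible post-baseline ECOG summary is a shift to the best score, which largely hides late or intermittent decline and depends on the number of visits

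*SAP*

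**What the plan says.** - **Status of ECOG.** The protocol summary lists "Eastern Cooperative Oncology Group (ECOG) performance status" under key safety assessments. Protocol 3.2.2.1 repeats this ("Safety assessments will include: physical examination with vital signs including body weight, ECOG performance status, and evaluation for AEs"), and so does the list in 6.6.
- **Collection.** Under Protocol 6.6.5, ECOG is scored at screening, before dosing on Day 1 of each cycle, at treatment discontinuation and at the safety follow-up visits. Protocol 3.2.3.1.1 gives azacitidine-alone subjects one follow-up visit (28 days). Protocol 3.2.3.1.2 gives combination subjects two (28 and 90 days).
- **Planned output.** SAP 10.3, in the efficacy section and on the ITT Population: "Shift tables from baseline to best post baseline in ECOG performance score will be displayed by disease cohort and treatment arm". No window is stated for the post-baseline period. The only other visible ECOG output is at baseline, in SAP 7.2: "Eastern Cooperative Oncology Group (ECOG) performance status (PS) and baseline electrocardiograms (ECGs) will be summarized".
- **Comparable safety measures.** SAP 12.2: "Shifts from baseline to the worst grade observed during the treatment for selected laboratory results will also be provided". SAP 12.4 tabulates vital signs with "shifts from baseline to worst during treatment". SAP 12 sets the population: "All summaries of safety data will be conducted using the Safety Population".

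**The concern.** Comparing the tolerability of the two regimens is a secondary objective. For a repeated safety measure, the question is how far subjects deteriorate. A best-score table answers a different one: whether the subject was ever as good as, or better than, at entry. One acceptable score, usually an early one, outweighs any later decline. The other repeated safety measures in this SAP are shifted to the worst value, and no reason is given for treating ECOG differently.

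There is also a comparability problem. The minimum of several scores falls as more scores are taken, even when function does not change. Treatment is open-ended after Cycle 6, and the follow-up schedule differs by arm, so the arms need not contribute equal numbers of scores. At stake is a descriptive safety table that could understate functional decline in both arms and compare them unevenly.

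**Working it through.** The documents give no figure for ECOG, so there is none to reproduce. The check has three parts.

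**1. Number of scores per subject.** For a subject who stops after six cycles, Cycle 1 Day 1 (pre-dose) serves as baseline. The post-baseline scores are Day 1 of Cycles 2 to 6 (5), the discontinuation visit (1) and follow-up (1 on azacitidine alone, 2 on the combination).

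- Azacitidine alone: 5 + 1 + 1 = 7.
- Combination: 5 + 1 + 2 = 8.

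**2. How much deterioration the best-score table shows.**

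*Lasting decline.* Assume it starts at a visit chosen uniformly from 1 to k, with scores at baseline level before that. The best score is worse than baseline only if the decline starts at visit 1, so the share of decliners shown is 1/k: 1/7 = 14%, 1/8 = 12.5%, 1/12 = 8%. A worst-score table shows 100%.

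*Intermittent decline.* Assume each visit is worse than baseline with probability 0.5, and k = 7.

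- Independent visits: the best table shows 0.5^7 = 0.8% of subjects as worse; the worst table shows 1 − 0.5^7 = 99.2%.
- Within-subject correlation 0.5 (beta-binomial): 20.9% against 79.1%.

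**3. Effect of visit count when function does not change.** Let q be the assumed chance that a visit is scored better than baseline by error, and ρ the assumed within-subject correlation. Neither is in the documents. For baseline 1 or 2, the chance of appearing improved is

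- independent visits: 1 − (1 − q)^k;
- correlated visits: 1 − B(a, b + k)/B(a, b), where B is the beta function, a = q(1 − ρ)/ρ and b = (1 − q)(1 − ρ)/ρ.

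A subject with baseline 0, who is eligible under inclusion criterion 2, cannot appear improved. Entries are percentages; differences are in percentage points.

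| q | ρ | k = 7 | k = 8 | Difference | k = 6 | k = 12 | Difference |
|---|---|---|---|---|---|---|---|
| 0.02 | 0 | 13.2 | 14.9 | 1.7 | 11.4 | 21.5 | 10.1 |
| 0.05 | 0 | 30.2 | 33.7 | 3.5 | 26.5 | 46.0 | 19.5 |
| 0.10 | 0 | 52.2 | 57.0 | 4.8 | 46.9 | 71.8 | 24.9 |
| 0.15 | 0 | 67.9 | 72.8 | 4.9 | 62.3 | 85.8 | 23.5 |
| 0.05 | 0.3 | 16.9 | 17.9 | 1.0 | 15.7 | 21.2 | 5.5 |
| 0.05 | 0.5 | 12.3 | 12.9 | 0.6 | 11.7 | 14.5 | 2.8 |

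The 7-against-8 columns follow from the schedule. The 6-against-12 columns are illustrative only, since no document predicts such a difference between arms.

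**Check on the remedy.** A worst-of-k score has the same dependence. With a 0.10 chance per visit of a spuriously worse score and independent visits, 1 − 0.9^7 = 52.2% and 1 − 0.9^8 = 57.0%. A worst-score table therefore restores deterioration but does not remove the visit-count effect.

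**The case against.** The strongest defence is that ECOG is not a named endpoint. The secondary safety endpoint in both documents covers adverse events and clinical laboratory evaluations. Protocol 9.7 lists what will be tabulated ("Adverse events, vital sign measurements, physical exam findings, clinical laboratory data, ECG interpretations, pregnancy tests for FCBP" and concomitant treatments) without ECOG, so the SAP does not drop a promised safety table. ECOG sits in the SAP's efficacy section, where a best-value summary parallels best overall response. Tolerability is mainly read from treatment-emergent events by maximum grade, serious events, events leading to discontinuation, reduction or interruption, and deaths. Clinically significant worsening of a pre-existing condition counts as an adverse event under Protocol 10.1. All of this stands and limits the importance of the point. It does not make a best-score shift informative about decline in a measure the protocol three times calls a safety assessment.

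Three stronger readings are tempting, and the documents do not support them.

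- *That deterioration is invisible.* It is not: a subject whose every post-baseline score is worse than baseline is shown as worse. Early sustained decline appears; late or intermittent decline largely does not.
- *That no other post-baseline ECOG summary exists.* Text is blacked out directly after the sentence in SAP 10.3, between 12.2 and 12.4, and after 12.5. The statement can cover visible text only.
- *That the table builds in a bias of 20 to 25 points towards the arm with more visits.* That size needs independent visits, an assumed error rate of about 5% or more, and twice as many visits in one arm. Repeated scores in one subject are likely to be correlated, and with ρ = 0.5 and q = 0.05 the 6-against-12 gap is 2.8 points.

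**Conclusion.** The concern holds in a limited form. As far as the published text shows, following the SAP produces a post-baseline ECOG table that largely hides late or intermittent decline, against the convention the SAP applies to laboratory grades and vital signs. The 1/7 figure rests on a lasting decline with uniformly distributed onset.

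The dependence on visit count is real, but its size is uncertain. The one scheduled extra visit on the combination is worth roughly 1 to 5 points for q between 0.02 and 0.15, and under 1 point with ρ = 0.5 and q = 0.05. Anything larger depends on treatment duration as observed, so which arm would benefit cannot be stated in advance. The consequence is confined to descriptive safety reporting. The response-rate analysis, its power and the primary conclusion are untouched.

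**What to change.** In SAP 10.3:

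1. Add a shift from baseline to worst post-baseline ECOG on the Safety Population, with one stated post-baseline window common to both arms, for example through 28 days after the last azacitidine dose. State how combination subjects who stop azacitidine but continue durvalumab are handled. The change of population is mainly for consistency with SAP 12, since undosed subjects will have few or no post-baseline scores.
2. Because the worst score also grows with visits, add shifts at fixed time points, for example Cycle 4 Day 1 and Cycle 7 Day 1, and at the Treatment Discontinuation Visit. Use all treated subjects as the denominator, with dead, off-treatment and missing as explicit categories. This matters most at Cycle 7 Day 1, which only subjects meeting the continuation criteria (Protocol 3.2.2.3 and 6.7.4) reach; a table of attenders alone would be selected on benefit.
3. Keep the best-score table as a supplement.

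The cost is two or three descriptive tables from data already collected, with no effect on alpha, sample size or trial conduct.

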11. PHARMACOKINETIC ANALYSIS

Pharmacokinetic concentration data and summary statistics will be tabulated. The PK, pharmacodynamics, demographic, safety, and efficacy data collected in this study may be combined with similar data from other studies and explored using population PK and/or PK-pharmacodynamic methods. A separate SAP will provide the details of the statistical methods used to analyze PK data. The results of such an analysis will be reported in a separate report.

12. SAFETY ANALYSIS

This section defines the safety parameters for the study. All summaries of safety data will be conducted using the Safety Population. Descriptive statistics will be provided by disease cohort and treatment arm.

12.1. Adverse Events

All safety analyses will be conducted using the Safety Population. All analyses will be presented by disease cohort and treatment arm within each disease cohort. Adverse events will be coded according to the MedDRA Version 19.0 or higher. The intensity of AEs will be graded according to the Common Terminology Criteria for Adverse Events (CTCAE) Version 4.03 or higher.

If a subject experiences multiple AEs under the same PT (SOC), then the subject will be counted only once for that PT (SOC). If a subject experiences the same AE more than once with a different intensity grade, then the event with the highest grade will be tabulated in “by grade” tables. In addition, AEs with a missing intensity will be presented in the summary table as an intensity category of “Missing” and will not be imputed.

Treatment emergent adverse events (TEAEs) are defined as AEs **occurring** or worsening on or after the date of the first dose of the study treatment (durvalumab or azacitidine) and within 90 days after last dose of durvalumab or 28 days after last dose of azacitidine, **as well as those serious TEAEs made known to the investigator at any time thereafter that are suspected of being related to study treatment**. A treatment-related TEAE is defined as a TEAE where the causal relationship was assessed by the investigator as “Suspected”. If the relationship between a TEAE and a study drug is missing, the TEAE will be considered to be related to the study treatment.

Tables summarizing the incidence of TEAEs by disease cohort and treatment arm will be generated with the following:

- TEAEs;
- TEAEs related to azacitidine, durvalumab and azacitidine and/or durvalumab;
- TEAEs of CTCAE grade 3
- TEAEs of CTCAE grade 4
- TEAEs of CTCAE grade 3 or 4;
- TEAEs related to azacitidine, durvalumab and azacitidine and/or durvalumab with CTCAE grade 3
- TEAEs related to azacitidine, durvalumab and azacitidine and/or durvalumab with CTCAE grade 4
- TEAEs related to azacitidine, durvalumab and azacitidine and/or durvalumab with CTCAE grade 3 or 4;
- TEAEs with CTCAE grade 5;

- TEAEs with CTCAE grade 5 related to azacitidine, durvalumab and azacitidine and/or durvalumab;
- Serious TEAEs;
- Serious TEAEs related to azacitidine, durvalumab and azacitidine and/or durvalumab;
- TEAEs leading to discontinuation of azacitidine, durvalumab and azacitidine and/or durvalumab;
- TEAEs leading to dose reduction of azacitidine;
- TEAEs leading to dose interruption of azacitidine, durvalumab and azacitidine and/or durvalumab;
- TEAEs leading to infusion interruption of durvalumab.

As well as

- TEAEs by cycle of onset;
- Serious TEAEs by cycle of onset;
- TEAEs related to azacitidine, durvalumab and azacitidine and/or durvalumab, by cycle of onset;
- TEAEs of CTCAE grade 3 by cycle of onset
- TEAEs of CTCAE grade 4 by cycle of onset;
- TEAEs of CTCAE grade 3 or 4 by cycle of onset;
- TEAEs by maximum CTCAE grade;
- TEAEs related to azacitidine, durvalumab and azacitidine and/or durvalumab, by maximum CTCAE grade;
- Common ($\geq 10\%$) TEAEs;
- Common ($\geq 10\%$) TEAEs related to azacitidine, durvalumab and azacitidine and/or durvalumab;
- By age category: <65 , $65-74$, ≥ 75
- By gender

Unless otherwise stated, TEAEs will be presented by MedDRA SOC and PT. To facilitate clinical study report writing the following tables will be produced

- TEAEs by PTs
- TEAEs by SOCs
- TEAEs related to azacitidine, durvalumab and azacitidine and/or durvalumab by PTs
- TEAEs related to azacitidine, durvalumab and azacitidine and/or durvalumab by SOCs
- TEAEs of CTCAE Grade 3 or 4 by PTs, by Grade (3 and 4 separately) and combined (3 or 4 combined)

- TEAEs of CTCAE Grade 3 or 4 by SOCs, by Grade (3 and 4 separately) and combined (3 or 4 combined)
- TEAEs related to azacitidine, durvalumab and azacitidine and/or durvalumab of CTCAE Grade 3 or 4 by PTs, by Grade (3 and 4 separately) and combined (3 or 4 combined)
- TEAEs related to azacitidine, durvalumab and azacitidine and/or durvalumab of CTCAE Grade 3 or 4 by SOCs, by Grade (3 and 4 separately) and combined (3 or 4 combined)

All deaths, on treatment deaths, off treatment deaths and causes of death will be summarized. On treatment deaths are defined as deaths occurring within 90 days after the last dose of durvalumab or 28 days after last dose of azacitidine. Off treatment death are defined as deaths occurring after that period. These summaries will be based on the death eCRF page.

Individual subject listing of AEs will be presented. In addition, the following tabulated lists will be provided:

- Listing of SAE;
- Listing of TEAEs leading to permanent withdrawal of any study drug
- Listing of all TEAEs with outcome of death
- Listing of all subjects who died

Adverse events of special interests (AESI)

The adverse events of special interest (AESI) refer to a group of PTs from one or more SOCs relating to a defined medical condition or area of interest. Unless an AESI is defined by a single PT the AESI generally refers to a group of PTs, rather than the individual PTs.

AESIs will be summarized separately for azacitidine and durvalumab, The AESI summary for each study treatment will be summarized by AESIs, which will be referred as AESI categories in tables and listings, and by PT.

The following AESIs for azacitidine based on risk definitions (search criteria) as outlined in the Vidaza risk management plan (RMP) currently approved at the time of data cut-off will be summarized:

- Myelosuppression (Neutropenia, thrombocytopenia, anemia, general myelosuppression)
- Hemorrhagic events
- Infections
- Renal failure
- Hepatic failure
- Ischemic colitis
- Interstitial lung disease
- Cardiac events (cardiac failure, cardiac arrhythmias, myocardial infarction)
- Anxiety, confusional state, insomnia

- Other psychiatric disorders
- Tumour lysis syndrome
- Gastrointestinal disorders as defined by MedDRA SOC

Below are the AESIs for durvalumab for regulatory purposes:

- Adrenal insufficiency
- Colitis
- Dermatitis
- Diarrhoea
- Diabetes Mellitus Type 1
- Hyperthyroidism
- Hypophysitis
- Hypothyroidism
- Infusion related/Hypersensitivity/Anaphylactic reactions
- Select renal events
- Select pancreatic events
- Pneumonitis
- Rash
- Select hepatic events
- Other rare/miscellaneous

After review of the data, there may be other AESIs identified. The following summaries will be provided for TEAEs included in the above-mentioned AEs of special interest:

- All TEAEs
- All TEAEs by cycle of onset
- TEAEs of Grade 3
- TEAEs of Grade 4
- TEAEs of Grade 3 or 4
- Serious TEAEs
- TEAEs leading to study drug withdrawal
- TEAEs leading to study drug dose reduction
- TEAEs leading to study drug dose interruption

- TEAEs leading to death

The incidence rate per 100 person-years will also be derived for each AESI.

